## Background

Crohn's disease (CD) is a chronic inflammatory bowel disease (IBD) most often diagnosed in young adults. The etiology is unknown, but CD is thought to arise from a dysregulated interaction between the gut microbiome and the mucosal immune system in a genetically predisposed individual. The incidence in Denmark continues to increase and is among the highest in the world. The current incidence is 9.1/100,000/year corresponding to approximately 500 patients diagnosed each year and up to 18,000 persons living with CD.

Typical symptoms are chronic diarrhea, abdominal pain, and weight loss. A subgroup of patients experience extra-intestinal disease such as arthritis, uveitis, pyoderma gangrenosum, erythema nodosum, or primary sclerosing cholangitis. CD is characterized by recurrent disease activity and a strong tendency to relapse after remission with medical treatment (immunosuppressants) or surgical resection. A small proportion of patients experience continuous disease activity.

Cardinal lesions are mucosal ulcerations ranging from small aphthous ulcerations to large ulcers and fissures. Histologically, the inflammation is transmural and often granulomatous. Typically, CD has a segmental distribution, and the entire gastrointestinal tract may be involved. The disease is often located in the terminal ileum and right colon (ileocecal CD). In approximately one third of patients, the disease is located in the small intestine, and one third has CD restricted to the colon. At the time of diagnosis, the majority of patients have an inflammatory phenotype, i.e. mucosal ulcerations without stricture, fistula, or abscess. In 10-30% of patients, however, strictures of varying degrees are present at debut; primarily in patients with CD in the small bowel.

## Current guidelines for diagnosing Crohn's disease

Most patients have CD located within reach of the colonoscope, and ileocolonoscopy (IC) with segmental biopsies is currently the first-line diagnostic procedure in patients with clinically suspected CD. Regardless of findings at IC, however, an additional small bowel examination is recommended for evaluation of disease extension (e.g. MR enterography or small bowel capsule endoscopy). IC is invasive and reaching the terminal ileum is not always possible. Although significant adverse events such as bleeding and perforation are rare (< 0.1%), up to one third of the patients experience minor adverse events (e.g. abdominal pain and bloating), and patients prefer less invasive modalities.

Fecal calprotectin is an established clinical biomarker for IBD, and it is helpful in selecting patients for further diagnostic workup. Concentrations found in healthy individuals range between 10 and 50 mg/kg stool, and a fecal calprotectin concentration of  $\leq 40$  mg/kg confers a  $\leq 1\%$  probability of having IBD. Several studies implicated that fecal calprotectin allowed differentiation between non-IBD and IBD at a cut-off between 100

and 200 mg/kg. However, an exact cut-off value for the discrimination between IBD and functional bowel disease is not established.

### **Modalities for minimally invasive diagnosis**

Technological advances have recently improved minimally invasive modalities for diagnosing and monitoring CD. The primary modalities are capsule endoscopy (CE), MR enterography and intestinal ultrasound (IUS). All modalities can visualize both the small intestine and colon in one procedure.

Visualizing the transmural component of CD (e.g., bowel wall thickening and post-contrast enhancement) is a key element of cross-sectional imaging. However, patients with newly diagnosed CD most often have mucosal ulcerations, and over time, CD can progress to complicated disease involving the entire gut wall. Hence, the diagnostic performance of different modalities differs between patient groups – from mucosal lesions at debut best visualized by endoscopy to transmural or penetrating lesions in longstanding disease. Correspondingly, recent studies have found an insufficient sensitivity of cross-sectional imaging for the initial diagnosis of CD, especially for CD located in the colon.

### **Pan-enteric capsule endoscopy**

CE is a patient-friendly and minimally invasive procedure. Compared to cross-sectional imaging, CE allows direct and detailed evaluation of the gastrointestinal mucosa with detection of the earliest lesions of CD.

Using CE to evaluate the small bowel and colon in a single examination is an attractive diagnostic approach.

Pillcam colon capsule endoscopy (PCCE) was introduced in 2006 and a pan-enteric capsule endoscope is now available in clinical practice (PillCam™ Crohn's capsule, Medtronic, Dublin, Ireland).

Performing CE of the colon requires optimal cleansing, and the *European Society of Gastrointestinal Endoscopy* currently recommends a regimen consisting of polyethylene glycol (PEG) in two divided doses and a booster preparation for propulsion of the capsule through the gastrointestinal tract and maintenance of optimal bowel cleansing throughout the entire procedure. The extensive bowel preparation required to achieve sufficient image quality is a significant limitation. In a recent study by our group, the volume of PEG was the main factor affecting the image quality. Although few patients were able to ingest the recommended volume of PEG (2+2 L), the diagnostic yield for CD was not affected.

In a prospective study of patients with known CD, PCCE had a sensitivity of 86% for detection of ulcerations in the colon and terminal ileum, and lesions outside the reach of the colonoscope were detected in 15% of patients. There was a moderate correlation between PCCE and IC for assessment of disease severity.

*Leighton et al.* compared the diagnostic yield of pan-enteric CE with IC in 66 patients with known active CD. The per-subject diagnostic yield for CD lesions was 83.3% for CE and 69.7% for IC (incremental yield 13.6%

(95% CI, 2.6-24.7%). CE detected a greater percentage of lesions in each evaluated segment than IC. The overall per-segment diagnostic yield was 40.6% and 32.7%, respectively. In a more recent study by *Bruining et al.*, the sensitivity and specificity of CE for active enteric inflammation was 94% and 74%, respectively. The sensitivity of CE was superior to that of MRE for the proximal small bowel and similar for the terminal ileum. This study included patients with an established diagnosis of CD. A recent study by our group examined patients with clinically suspected CD going through their first diagnostic work-up. The sensitivity and specificity for diagnosing ileocolonic CD with MREC was 67.9% (CI 53.7–80.1) and 76.3% (CI 65.2–85.3) (terminal ileum 76.9% and 85.6%; colon 27% and 93%) compared to 87.5% (CI 73.2–95.8) and 87.8% (CI 78.2–94.3) with CE (terminal ileum 96.6% and 87.5%; colon 75.0% and 93.0%). The sensitivity of CE was superior to that of MREC ( $P = 0.02$ ). Furthermore, the level of patient discomfort was equal for CE and MREC and significantly less than for IC.

In a retrospective evaluation of histopathological findings, the additional information obtained from biopsies was limited after CE performed in patients with clinically suspected CD. Biopsies added new diagnostic information in only 6.5%, and CE as a single diagnostic procedure was feasible in the majority of patients. Biopsies are warranted, however, in patients with an atypical endoscopic appearance or suspected malignancy.

### **Reading the capsule examination with computer assistance**

Analysis of the CE videos is a time-consuming process. The use of artificial intelligence (AI) – especially deep learning techniques – has received much attention in recent years. Several clinical areas have been investigated, including the ability to analyze endoscopy images and assist in clinical decision making. A recent meta-analysis showed a high sensitivity and specificity of deep learning techniques for ulcer detection in the small intestine. In contrast, the ability of AI to diagnose CD in the large intestine has not been studied to the same extent. Therefore, our group have previously tested the ability of a deep-learning algorithm to detect CD lesions in single images of the small intestine or colon captured with CE, determine the localization of lesions and the ability to characterize lesions of different severity. We obtained excellent agreement with the clinical standard, and diagnostic accuracy is equally high for the small intestine and colon. In a recent validation study, we examined the diagnostic accuracy of AI-assisted CE reading for the detection of inflammatory bowel disease in full-length CE examinations in 131 patients with suspected CD. Videos were processed by an offline version of the deep learning solution AXARO® (Augmented Endoscopy, Paris, France). The AXARO® platform is based on: 1) a user-friendly human-machine interface that ensures efficient use of its modules; and 2) an AI core that ensures the different classification and detection tasks. The AI core of AXARO® was trained on annotated small bowel CE still frames from a multicenter database, CAD-CAP. The

output of this AI solution is single images of interest, with and without marking the region of interest. The study revealed that the employment of AI assistance in CE reading significantly reduced review time while maintaining a high diagnostic accuracy for detection of CD.

Deep learning approaches have great potential to help clinicians detect, localize and determine the severity of CD with CE. Existing data are promising, and AI may have a central role in the future of non-invasive diagnosis of CD with CE, although significant development and testing of the technology is needed before clinical use.

### **MR enterography**

Magnetic resonance imaging is characterized by the ability to visualize all manifestations of CD – luminal, mural and extraintestinal – with high tissue contrast and without ionizing radiation. MR enterography (MRE) is performed with oral and intravenous contrast. Typical manifestations of CD are ulcers, wall thickening, relative contrast enhancement, dilated vasa recta (Comb sign), enlarged mesenteric lymph nodes, stenosis, prestenotic dilatation, abscess, and fistula. MRE diagnoses CD in the small intestine with a moderate to high sensitivity, specificity and inter-observer agreement. In contrast, recent studies have demonstrated the significantly lower sensitivity of MRE (25-47 %) for diagnosing colonic CD manifestations compared to pan-enteric CE, IUS and IC. The wall thickness, relative contrast enhancement and the presence of ulcers and edema are independent predictors for endoscopic disease severity.

### **Ultrasound**

IUS is an attractive imaging modality as it is non-invasive, associated with minimal to no patient discomfort and does not expose the patient to ionizing radiation. Typical findings in CD are wall thickening, loss of wall stratification, reduced peristalsis, stenosis, prestenotic dilatation, creeping fat, fistula, and abscess. IUS is able to diagnose CD in the terminal ileum and colon with a moderate to high sensitivity and a high specificity, although its diagnostic value is highly operator dependent. Visualization of the proximal small bowel as well as segments of the intestine located in the pelvis may be difficult and the examination may be compromised by air-filled intestinal loops. The wall thickness and vascularization in affected bowel segments evaluated with Doppler IUS correlates with the endoscopic disease activity.

### **Small bowel patency**

In a recent meta-analysis by *Pasha et al.*, capsule retention occurred in 2.35% of patients examined for suspected CD, and retention rates of 4-13% have been reported in patients with symptomatic CD. Recent

data from centers with extensive experience in capsule endoscopy suggest even lower retention rates in patients with suspected CD of around 0,5 %.

Different methods exist to determine small bowel patency before CE: 1) clinically, 2) a dissolvable test capsule or 3) cross-sectional imaging. Symptoms suggesting small bowel obstruction are abdominal pain (typically postprandial), distension, nausea, and vomiting. If small bowel stenosis is not firmly excluded, the Pillcam patency capsule (Medtronic, Dublin, Ireland) can be used to confirm small bowel patency before performing CE. The patency capsule is a dissolvable capsule with the same size as the Pillcam SB3 capsule (26 x 11 mm). It is composed of a lactose body with barium added for radio opacity. In each end, the patency capsule has a timer plug designed to erode after 30 hours resulting in disintegration of the capsule, and it has been stated that all patency capsules are dissolved within 72 hours. Capsule endoscopy is considered safe if the patency capsule is excreted before 30 hours, an intact capsule is excreted after 30 hours, or passage to the colon of an intact patency capsule is radiologically confirmed.

*Herrerias et al.* examined the Pillcam patency capsule in 106 patients with radiographic evidence of a small bowel stricture. Small bowel patency was confirmed in 59, and none of these patients experienced capsule retention at a subsequent capsule endoscopy. No severe adverse events could be attributed to the patency capsule. Furthermore, *Yadav et al.* concluded that the Pillcam patency capsule and radiological examination were equally reliable for excluding small bowel obstruction or strictures. Hence, available studies suggest that the Pillcam patency capsule is a safe method for testing small bowel patency before capsule endoscopy, even in patients with a radiologically verified stenosis.

In a study evaluating the accuracy of MRE for prediction of patency capsule retention in patients with established small bowel CD, the sensitivity and specificity was 92.3% and 59%, respectively. If the decision to administer CE was based on imaging and not on patency capsule results, at least 40% of the patients would not have undergone CE. Hence, MRE is less accurate in the evaluation of functional small bowel patency, frequently overestimating the risk of obstruction.

Use of IUS in predicting capsule retention is less well studied, although a study of 50 patients with suspected small bowel stenosis found a sensitivity and specificity of 92.3% and 72.9%, respectively, for impassable stenosis at double-balloon enteroscopy.

## Future perspectives

Implementing pan-enteric CE as a first-line modality in patients with suspected CD could reduce the need for IC; changing IC from a first line procedure to a targeted procedure for obtaining biopsies or if CE is incomplete or contraindicated. Since pan-enteric CE visualizes the entire small bowel, this offers a potential single-examination strategy yielding the total disease distribution. This strategy might be feasible; especially in

young patients with low risk of neoplasia. The potential is a rapid and less invasive, better tolerated and possibly cost-effective diagnostic workup. Future research should develop new diagnostic algorithms using minimally invasive technology, examine the feasibility of CE as a first-line diagnostic procedure, reduce the time used for CE analysis (e.g., with AI), implementing pan-enteric activity scores, and optimize bowel preparation, which will add further potential to this modality. Cross sectional imaging should be reserved for more advanced stages of CD to harvest the full potential of this modality.

## **Hypothesis**

Pan-enteric CE is a feasible, safe and patient friendly first-line diagnostic procedure reducing the need for IC and additional diagnostic procedures in patients examined for clinically suspected CD.

## **Aim**

The aim of this study is to determine the feasibility, efficacy and safety of pan-enteric CE as the first-line diagnostic procedure compared to traditional diagnostic work-up with IC plus MRE or small bowel (SB)CE in patients with clinically suspected CD.

## **Inclusion criteria**

- Clinical suspicion of CD\*
- Age 18-40 years
- Signed informed consent

\*A clinical suspicion of CD is based on the following definition: Diarrhea and/or abdominal pain for more than 1 month (or repeated episodes of diarrhea and/or abdominal pain) and *either* fecal calprotectin  $\geq$  200 mg/kg *or* fecal calprotectin  $\geq$  50 mg/kg plus one or more of the following findings: (1) C-reactive protein (CRP)  $>$  5 mg/L, (2) thrombocytosis ( $>$  400 x 10^9/L), (3) anemia (hemoglobin  $<$  7.0 mmol/L for women and  $<$  8.0 mmol/L for men *or* a decrease  $>$  0.5 mmol/L compared to the usual level), (4) prolonged fever ( $>$  37.5 °C for more than 2 weeks), (6) weight loss ( $\geq$  3 kg *or*  $\geq$  5% compared to the normal body weight), (7) perianal abscess / fistula *or* (8) a family history of inflammatory bowel disease.

[figure not shown]
## **Exclusion criteria**

- Previous intestinal resection
- Positive serologic markers for celiac disease
- Positive stool polymerase chain reaction for pathogenic bacteria
- Positive stool polymerase chain reaction for intestinal parasites

- Suspected or established acute bowel obstruction (ileus)
- Intake of NSAIDs or acetylsalicylic acid  $\leq$  4 weeks before inclusion, except low-dose, prophylactic acetylsalicylic acid ( $\leq$  150 mg per day)
- Intake of opioid or opioid-like medication  $\leq$  1 week before inclusion
- Pregnancy or lactation
- Unable to comply with protocol requirements, e.g. for reasons including alcohol or recreational drug abuse
- Known gastrointestinal disorder other than functional gastrointestinal disorders
- Renal failure defined by a plasma-creatinine above the normal reference range

## Study design

This is a pragmatic, prospective, randomized multicenter study comparing a new minimally invasive diagnostic algorithm with the traditional diagnostic work-up in patients with clinically suspected CD. Patients referred to medical gastroenterology units at public hospitals in the Region of Southern Denmark are screened for participation in the study at the time of referral from primary care or after the first diagnostic interview. Participation from centers outside the Region of Southern Denmark is possible if a physician responsible for the project can be appointed and centers are able to comply with the protocol requirements. Each patient will complete a standardized work-up including medical history, physical examination, blood samples and fecal calprotectin. Patients are randomized 2:1 stratified by participating center to a minimally invasive strategy with pan-enteric CE (Pillcam Crohn's) or IC plus MRE or SBCE. All examinations are reviewed and described in a standardized fashion.

## Endpoints

*Primary endpoint:*

1. Diagnostic completeness, defined as the proportion of patients in each group achieving a complete gastrointestinal assessment and an unambiguous diagnosis after the first-line work-up strategy without need for supplementary examinations.

*Secondary endpoints:*

1. Feasibility of pan-enteric CE: Number of patients with suspected CD examined with pan-enteric CE and the number of ICs avoided
2. Additional examinations: Need for additional examinations in the two randomization arms
3. Safety: Number of severe adverse events, delayed or missed diagnoses
4. Time to diagnosis: Time from referral or first diagnostic procedure to a final diagnosis and treatment
5. Disease classification and medical treatments in the two randomization arms
6. Patient satisfaction: Difference in Gastrointestinal Endoscopy Satisfaction Questionnaire (GESQ) score
7. Costs: Expenditure on diagnostic procedures, treatment and loss of productivity
8. Artificial intelligence: Diagnostic utility of AI algorithms in detection of gastrointestinal pathology using pan-enteric CE – sensitivity, specificity, severity, prediction and impact on clinical decision making

## **Logistics**

### *Subject identification and informed consent process*

Subjects are identified either by physicians at trial sites when screening referrals to the trial sites on suspicion of inflammatory bowel disease or at the first interview with the treating physician, if the suspicion of inflammatory bowel disease is first raised here.

Blood samples, including serologic markers for celiac disease, and stool polymerase chain reaction for pathogenic bacteria and parasites are performed in accordance with the standard of care for newly referred patients at the site of inclusion. If fecal calprotectin is performed  $\leq$  4 weeks prior to enrollment in the study, a repeated test is not mandatory.

Regardless of how the subject is identified, the subject will be offered inclusion in the trial at the first interview with the treating physician, if the inclusion criteria and none of the exclusion criteria are met. Oral and written information is provided by the treating physician at the trial site, who has been delegated to do so by the principal investigator by written agreement.

Since oral and written information is provided at a scheduled interview with the treating physician in a gastroenterology outpatient clinic, the interview takes place undisturbed and the subject has the opportunity to bring an assistant to the interview. The subject will also be informed that there is an opportunity to request a cooling-off period or a new interview with a repetition of the oral information in the presence of an assistant. If the subject does not want a cooling-off period, consent is sought immediately, otherwise after at least 24 hours of cooling-off period. The declaration of consent is signed by the patient and the treating physician.

#### *Baseline visit*

Patients undergo a full medical history taking and physical examination by a physician. Patients are randomly allocated to a minimally invasive or standard diagnostic algorithm using block randomization in groups of two.

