#### *Minimally invasive diagnostic work-up*

Pan-enteric CE is performed at the center from which the patient is included. Before CE, patients are evaluated for small bowel patency with a thorough clinical assessment, supplemented with the patency capsule system if deemed necessary. Assessment of small bowel patency can be supplemented with IUS prior to examination with the patency capsule in centers with experience in this procedure. If bowel patency is confirmed, pan-enteric CE is performed using standard bowel preparation as described below. If bowel patency is not confirmed, the patient will cross over to a standard diagnostic work-up with IC plus MRE. If the capsule fails to pass from the stomach to the duodenum during the examination, the procedure will be considered failed and the patient will cross over to a standard diagnostic work-up. Endoscopic delivery of the capsule to the duodenum is not permitted in this study.

CE is analyzed by central reading performed by an expert reader and lesions of interest are confirmed and countersigned by a second expert. In case of disagreement between the first and second expert on findings or clinical recommendation after the examination, an evaluation committee of several expert readers will provide a final decision. Results are reported standardized as described below, and the treating

gastroenterologist is provided with the result. Decisions regarding diagnosis, additional diagnostic work-up and treatment are made afterwards by the treating physician.

[figure not shown]

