### *Sample size calculation*

In a randomized controlled non-inferiority trial with a 2:1 ratio of patients examined with CE and standard diagnostic procedures (IC + MR enterography or SBCE), significance level 0.05, power 0.8, expected diagnostic completeness in samples 0.65, expected diagnostic completeness in controls 0.77 and a margin on risk difference scale 0.3, the following number of patients are required to show non-inferiority between two diagnostic strategies: 165 (110 in CE arm and 55 controls).

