## **Data capture and randomization**

Data are collected and stored in a secured REDCap database under OPEN (Open Patient data Explorative Network). REDCap also provides a tool for 2:1 randomization of patients for minimally invasive diagnosis or standard diagnostic work-up, respectively.

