## BUDGET- OG FINANSIERINGSPLAN

Projekttitel: Feasibility of a non-invasive diagnostic algorithm in suspected Crohn's disease – a prospective comparison of pan-enteric capsule endoscopy versus ileocolonoscopy plus MR enterography or small-bowel capsule endoscopy										
Budgetpost	Enhed	Udgift	Antal	Samlet beløb	Region Syddanmarks ph.d.-pulje	Syddansk Universitet - Institut for Regional Sundhedsforskning	Region Syddanmarks pulje for Fri- og Strategisk Forskning	Aage og Johanne Louis-Hansens Fond	Andre fonde	
Aflønning										
[name], ph.d. års værk inkl. studieafgift	År	623.333,33	3	1.870.000,00	610.000,00	400.000,00	0,00	650.000,00	210.000,00	
Projektkordinator - deltidssat sygeplejerske	År	200.000,00	2	400.000,00	0,00	0,00	400.000,00	0,00	0,00	
Drift										
Pillcam Crohns (kamerapille)	Stk.	5.600,00	110	616.000,00	0,00	0,00	0,00	616.000,00	0,00	
Pillcam Patency capsule (selvoplosgelig testkapsel)	Stk.	500,00	20	10.000,00	0,00	0,00	1.000,00	9.000,00	0,00	
Bistand fra OPEN og statistiker				20.000,00	0,00	0,00	20.000,00	0,00	0,00	
Kurser og konгрesser				20.000,00	0,00	0,00	20.000,00	0,00	0,00	
Besøg ved udenlandsk forskningsenhed				30.000,00	0,00	0,00	0,00	0,00	30.000	
Udgifter til publikation				30.000,00	0,00	0,00	30.000,00	0,00	0,00	
Andet										
Patientbefordring				50.000,00	0,00	0,00	50.000,00	0,00	0,00	
I alt				3.046.000,00	610.000,00	400.000,00	521.000,00	1.275.000,00	240.000	
Total budget										kr 3.046.000,00
Fondene markeret med grønt har bevilget penge til projektet										

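### Blocks of two cannot deliver the 2:1 allocation on which the trial is designed and sized

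*Protocol*

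**What the plan says.** The Baseline visit section of the protocol (under Logistics) describes the act of allocation and gives the only block length in the document: patients are assigned to one of the two algorithms "using block randomization in groups of two". It states no ratio.

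Three other sections state the ratio, and they agree:

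- Study design: "Patients are randomized 2:1 stratified by participating center".
- Sample size calculation: a non-inferiority trial "with a 2:1 ratio of patients examined with CE and standard diagnostic procedures", with the requirement given as "165 (110 in CE arm and 55 controls".
- Data capture and randomization: "REDCap also provides a tool for 2:1 randomization of patients".

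The budget is consistent with 2:1. The line "Pillcam Crohns (kamerapille" lists 110 units at 5,600 kr, which is 616,000 kr.

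Two sections bear on concealment. Under Subject identification and informed consent process, "the subject will be offered inclusion in the trial at the first interview with the treating physician". Under Minimally invasive diagnostic work-up, once the capsule report is available, "Decisions regarding diagnosis, additional diagnostic work-up and treatment are made afterwards by the treating physician".

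**The concern.** A permuted block that balances at 2:1 must have a length divisible by three. A length of two balances only at 1:1. The block length in the Baseline visit section and the ratio in the other three sections therefore cannot both be followed, and someone building or auditing the allocation list has no consistent specification to work from.

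Two things would be at stake if the list were built in blocks of two. First, the arms would be close to equal, so the CE arm would fall well short of 110. Feasibility of pan-enteric CE and the accuracy of the AI reading are estimated in that arm alone.

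Second, concealment would be weak. The procedure a patient receives reveals the arm, allocation is stratified by center, and the block length is printed in a document that sites hold. A recruiter who tracks the center's allocations would know the second assignment of every block before offering inclusion. The primary endpoint requires a complete and unambiguous work-up with no further examinations needed. Selecting which patients enter when the next arm is known could therefore shift it. The document gives no basis for sizing such a bias, and none is claimed.

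**Working it through.** **1. Which ratio the sample size uses.** Inputs from Sample size calculation: completeness 0.65 (CE) and 0.77 (control), margin 0.30, significance level 0.05, power 0.80, ratio 2:1. Sidedness is not stated; one-sided 0.05 is assumed. With unpooled variance, the control arm needs

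n = [p_C(1 − p_C) + p_E(1 − p_E)/r] × (z₀.₉₅ + z₀.₈₀)² / (margin − difference)²

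Here p_C(1 − p_C) = 0.77 × 0.23 = 0.1771, p_E(1 − p_E) = 0.65 × 0.35 = 0.2275, and margin − difference = 0.30 − 0.12 = 0.18.

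- r = 2: n = 55.5 controls, 166.5 in total (56 + 112 = 168 after rounding up). This is within 3% of the stated 165.
- r = 1: n = 77.2 per arm (78 + 78 = 156).

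Other variants at 2:1 do not come close: one-sided 0.025 gives 213, pooled variance 184, a continuity correction 191, and null-restricted (Farrington-Manning) variance 149. So 165 is a 2:1 figure.

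**2. What a block of two can contain.** The possible blocks are CE-CE, CE-control, control-CE and control-control, with CE shares of 1, 1/2, 1/2 and 0. None is 2/3. Balanced blocks are 1:1, and 165 patients then split 82/83.

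**3. Effect on precision and power.** SE = √(0.2275/n_E + 0.1771/n_C); power = Φ(0.18/SE − 1.645).

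| CE / control | SE | Power |
|---|---|---|
| 110 / 55 | 0.0727 | 79.7% |
| 82 / 83 | 0.0701 | 82.2% |

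At one-sided 0.025 the order is the same: 69.7% and 72.9%. For CE-only estimates the SE ratio is √(110/82.5) = 1.155, about 15% larger. The CE arm loses 27 to 28 of 110 patients, or 25%.

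**4. Allocations fixed in advance.** Assume the block length is known and the center's past allocations are seen.

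- 1:1 blocks of two: the second of each pair is certain, so 1/2 = 50%.
- 2:1 blocks of three: in CE-CE-control and CE-control-CE only the third is certain; in control-CE-CE the second and third are. The mean is (1 + 1 + 2)/3 = 4/3 per block, and (4/3)/3 = 44%.
- 2:1 fixed blocks of six and nine: 29% and 21%.

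A fixed length of three restores the ratio but hardly improves concealment.

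**5. If some patients were already allocated 1:1.** The counts k are assumptions for illustration. With the table corrected after k patients and N held at 165, the CE arm is k/2 + (165 − k) × 2/3.

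| k | CE / control | Power | Share of arm enrolled after correction, CE − control |
|---|---|---|---|
| 30 | 105 / 60 | 80.8% | 0.857 − 0.750 = 0.107 |
| 60 | 100 / 65 | 81.6% | 0.700 − 0.538 = 0.162 |
| 90 | 95 / 70 | 82.1% | 0.526 − 0.357 = 0.169 |

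If completeness changed by 10 percentage points between the periods (also assumed), a comparison ignoring period would be off by 1.1, 1.6 or 1.7 points.

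**The case against.** The strongest reply is that the Baseline visit sentence states no ratio and may simply be a clumsy way of saying that patients are randomized into two groups. Every section that does state a ratio says 2:1, the REDCap tool is described as 2:1, and the capsule order matches. On that reading nothing is wrong but one phrase, and the predictability argument concerns a list that probably does not exist. Even correct blocks of three would leave 44% of allocations foreseeable, so predictability comes mainly from short fixed blocks, not from the contradiction. Primary power is not harmed in either case, and the mid-trial scenarios are assumed.

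Much of this stands. The document favors 2:1, the consequences are conditional, and the primary analysis keeps its power. Two further points limit the concealment argument. The treating physician's later decisions are made with the procedure known whatever the block length, so they matter here only because patient selection at entry could affect them. CE findings are also read centrally with a second expert, and with a committee if the two disagree, while eligibility rests mainly on laboratory criteria.

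The reply does not remove the error. The sentence is the operational instruction for allocation and the only one that gives a block length. Read in the ordinary sense it cannot produce 2:1, and the protocol alone cannot show how the table was built. Nor is this a detail left for another document: the protocol states a block length, and it conflicts with the stated ratio.

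**Conclusion.** The concern holds. The block length in the Baseline visit section is incompatible with the 2:1 ratio used everywhere else, and it is that section which needs correcting, since the stated sample size is recovered only at 2:1 among the variants tried.

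That the text is inconsistent is certain; the practical consequence is not. If the live table is already 2:1, only the wording is wrong. If it was built in 1:1 blocks of two, the trial would end with a CE arm about a quarter smaller than planned, less precise CE-only secondary results and half its allocations open to prediction, but with no loss of primary power. The power figures assume a one-sided 0.05 test with unpooled variance. The predictability figures assume that staff know the block length and track their center's allocations. The point should be fixed, but it does not invalidate the design.

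**What to change.** In the Baseline visit section, replace the block phrase with wording such as: *in a 2:1 ratio, using permuted blocks whose length varies at random among multiples of three, stratified by center*. Record the actual lengths in a restricted randomization document that site staff cannot see. Have someone with no recruiting role check the ratio and block lengths in the live REDCap table. Then:

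- **Table already 2:1:** change the wording only. If the lengths are fixed and short, vary them from the next block onward. The cost is one amended sentence and the check.
- **Any patients allocated 1:1:** correct the table from the next block, restate the expected arm sizes in Sample size calculation, and stratify the primary risk difference by allocation period. The added cost is a regenerated table, the restated numbers and one extra stratum.

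The one statistical downside of longer, varying blocks is a slightly greater chance imbalance in very small centers.
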